4.6. Adverse event reporting

Adverse events will be self-reported by patients during the standard online follow-up. Adverse events (AEs) will be monitored and defined as any new medical condition or exacerbation of an existing condition as reported by the participants during the study.

Questioning of AEs will occur at all follow ups. Serious AEs will also be monitored and are defined as any untoward medical occurrence that results in death, is life threatening, requires hospitalisation or results in significant disability. We will comply with relevant Australian guidelines and requirements for reporting AEs ²⁴.

4.7. Data management

The data for the current study will primarily be collected and stored in REDCap software. This includes the patient baseline questionnaire (including online consent) and follow up data collected at 2-weeks, 6 weeks, 3-, 6-, 9-, and 12-months. These data will remain secure in REDCap during the period of the study. All participants will be allocated a de-identification code at the time of study enrolment. This will be a sequential enrolment number and contain no identification information. However, the identifiable data (e.g email and address) will be in the REDCap data base with non-identifiable data. The Primary investigator will control access to different data within REDCap for study investigators with different roles, ensuring only essential data are accessed by each investigator. At the completion of the study the non-identifiable data will be exported as an excel file including the de-identifiable code (Participant ID). A separate coding file will also be exported which would enable re-identification if required. These 2 files will be stored on SharePoint under different directories and only the data custodians ([name] and [name]) will have access to the coding file enabling re-identification.

We will also collect a small amount of hard copy data (e.g. GP hard copy consent forms). The data will be stored in a locked filing cabinet in the primary investigator's locked office, or entered into a spreadsheet that is saved on a secure SharePoint folder. If a participant withdraws from the study all previously collected and de-identified data will remain in the study.

At the completion of the study, all data will be stored securely in perpetuity. The data collected in this study may be made available to other research groups, in a de-identified form, for future Human Research Ethics Committee approved research projects which are an extension of, or closely related to, this proposed study. A data sharing agreement will be required for any research team wishing to access the data. The data-sharing agreement will require a commitment to using the data only for specified research purposes, to securing the data appropriately and to destroying the data after a nominated period. A full data management plan will be lodged at Macquarie University.

4.8. Data analysis

4.8.1. Sample size calculation

We used the Teerenstra et al ²⁵ method to calculate the required number of clusters based on an ANCOVA analysis for the primary outcome (RMQ) at 3 months with the baseline measurement of RMQ as a covariate. A total of 18 clusters (9 per arm) with an average of 62 participants per practice (i.e. total 1,116 participants) achieves 90% power to detect a minimum clinically important mean difference (MCID) of 2.5 points ²⁶ (Cohen's d=0.4) using a two-sided $\alpha=0.05$ and assuming a standard deviation (SD) of 5.7 points based on pilot study data ²⁷, a conservative intra-cluster correlation coefficient of 0.1, a cluster

autocorrelation coefficient (correlation between cluster means at baseline and follow-up) of 0.5, and an individual autocorrelation coefficient (correlation between participant scores at baseline and follow-up) of 0.6 informed by our Canadian pilot study. To allow for 20% patient attrition at 12 months and the possibility of attrition of 2 sites, we will aim to recruit 20 clusters and an average of 78 participants per cluster (i.e., a total of 1,560 participants). In our Canadian pilot study, we achieved 11% patient attrition after 12 months, and lost no sites. We will also have 85% power to detect a MCID of 0.1 points on the EQ-5D-5L²⁸ (Cohen's $d=0.42$) assuming a SD of 0.24 points (informed by our pilot study) after accounting for attrition.

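### The stated 90% power for the RMQ with 18 practices relies on normal quantiles; on a t reference with 16 degrees of freedom it is about 85%, and about 89% if all 20 practices stay.

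*Protocol*

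**What the plan says.** Section 4.8.1 (Sample size calculation) uses a published "method to calculate the required number of clusters based on an ANCOVA analysis for the primary outcome (RMQ) at 3 months", with baseline RMQ as covariate. The target is a "minimum clinically important mean difference (MCID) of 2.5 points" at two-sided 5%, "assuming a standard deviation (SD) of 5.7 points based on pilot study data", with "a conservative intra-cluster correlation coefficient of 0.1", a cluster autocorrelation ("correlation between cluster means at baseline and follow-up) of 0.5") and an individual autocorrelation of 0.6. The result is given as: "A total of 18 clusters (9 per arm) with an average of 62 participants per practice (i.e. total 1,116 participants) achieves 90% power".

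To cover 20% patient attrition at 12 months and the possible loss of 2 sites, the target is 20 practices averaging 78 participants (1,560 in total). For the secondary quality-of-life outcome the section adds: "We will also have 85% power to detect a MCID of 0.1 points on the EQ-5D-5L", with an SD of 0.24 and after accounting for attrition. It gives no ICC or autocorrelation for that outcome. It mentions no degrees of freedom or other small-sample allowance for the number of practices.

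Section 4.2 randomises practices 1:1, and section 4.8.2 fits practice as a random effect in a REML mixed model.

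**The concern.** Practices are the randomised units, so the arm comparison rests on 9 against 9 site-level summaries however many patients each contributes. The between-practice variance has to be estimated from those few units. A two-sided 5% test that allows for this uses a t reference with about 18 − 2 = 16 degrees of freedom, whose critical value is 2.12 and not 1.96. A power figure based on 1.96 is too high at this number of practices.

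At stake is how a null result is read. At the protocol's own planning point of 18 practices, the type II error would be about 15% and not the stated 10%. It also changes the meaning of the two additional practices: they are presented as spare, yet without them the design falls about 5 points short of 90%.

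**Working it through.** **Inputs, all from section 4.8.1:** difference 2.5; SD 5.7; m = 62 per practice; k = 9 practices per arm; ICC 0.1; cluster autocorrelation 0.5; individual autocorrelation 0.6; two-sided 5%. Equal practice sizes are assumed, since the text gives only an average.

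**1. Variance**
- Design effect: 1 + (62 − 1) × 0.1 = 7.1
- Correlation of practice means between baseline and follow-up: r = (62 × 0.1 × 0.5 + 0.9 × 0.6) / 7.1 = 3.64 / 7.1 = 0.513
- Design effect after baseline adjustment: 7.1 × (1 − 0.513²) = 5.234
- SE of the difference: √(2 × 5.7² × 5.234 / (62 × 9)) = 0.781
- Noncentrality: 2.5 / 0.781 = 3.20

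**2. Reproducing the stated figure (normal quantiles)**
- Power: Φ(3.20 − 1.96) = 89.3%
- Participants per arm for 90%: 2 × (1.96 + 1.2816)² × (5.7/2.5)² × 5.234 = 572, and 572 / 62 = 9.22 practices

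The stated 90% is thus reproduced to within one point, with 9.22 taken as 9. The protocol does not name the reference distribution. That it was the normal one is inferred, because at 18 × 62 the t reference does not come near 90%.

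**3. The same design on a t reference.** Power is taken from the noncentral t distribution with 2k − 2 degrees of freedom.

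| Practices × participants | Situation | df | RMQ power |
|---|---|---|---|
| 18 × 62 | planning point | 16 | 85.2% |
| 18 × 78 | two sites lost, no patient loss | 16 | 86.0% |
| 20 × 62 | no site lost, 20% patient loss | 18 | 89.1% |
| 20 × 78 | no loss of any kind | 18 | 89.8% |

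Taking off one further degree of freedom for the baseline covariate, or two for covariate and stratum, changes the first row to 84.9% or 84.5%. At 62 per practice, the first whole number per arm to exceed 90% on this basis is 11 (92%). Patients per practice hardly matter at an ICC of 0.1; the number of practices sets the power.

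**4. EQ-5D-5L.** The difference is 0.1 and the SD 0.24. **Assumption:** the RMQ ICC and autocorrelations apply, because none are given for this outcome. With 62 per practice:
- 18 practices: noncentrality 3.04; 86.0% on normal quantiles, 81.5% on t (16 df)
- 20 practices: noncentrality 3.21; 85.8% on t (18 df)

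The result is sensitive to the assumption. With an ICC of 0.08 and all else unchanged, 18 practices give 88% on t; with 0.05 they give 97%.

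**The case against.** The strongest reply is that the planned trial has 20 practices, not 18. The protocol reports that its pilot lost no sites and 11% of patients at 12 months. With 20 practices and 69 participants each (78 × 0.89 = 69.4), t-based power is 89.4%, within a point of the claim. The ICC of 0.1 is also called conservative: at 0.08, 18 practices would give 91% on t. Both points stand, and they limit the practical consequence. They do not rescue the sentence as written, which attaches 90% to 18 practices at an ICC of 0.1.

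A reader might infer more than the document supports:
- **An arithmetic error.** There is none. The named method and inputs give 89.3%, and rounding 9.22 down to 9 costs only 0.7 of a point.
- **An EQ-5D-5L power of 81% as established fact.** That figure borrows the RMQ correlations. The printed 85% is also close to 20 practices on a t basis (85.8%), and the wording about attrition does not say whether two sites are taken as lost.
- **A wrong effect size.** 2.5 / 5.7 = 0.439, which is 0.4 to one decimal. The reproduction shows that 2.5 and 5.7 were used, so no calculation at exactly 0.40 is implied.
- **An analysis with an inflated false-positive rate.** A cut-off of 1.96 on 16 degrees of freedom has a size of 6.8%. However, section 4.8.2 does not say that such a cut-off will be used, and the degrees-of-freedom method can properly be left to the SAP.
- **A definite further loss from unequal practice sizes.** The protocol gives no measure of variation in size, so no figure can be put on it. Repeated measurements in the mixed model may recover a little power, also by an unknown amount.

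**Conclusion.** The point holds as a missing small-sample allowance. At the protocol's own inputs, 18 practices give about 85% power for the RMQ on a t reference, not 90%; all 20 give about 89%. None of the four retention cases above, from two sites lost to no loss at all, reaches 90%. The two additional practices are therefore needed to approach the stated power and are not purely attrition cover.

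The shortfall is about 5 points if two practices are lost and about 1 point if none are. This rests on an ICC of 0.1, equal practice sizes and 16 or 18 degrees of freedom.

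For the EQ-5D-5L the conclusion is conditional. If the RMQ correlations apply, the stated 85% holds on the t basis only if no site is lost; with a lower ICC it could hold with 18. The protocol should say which inputs were used.

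**What to change.** In section 4.8.1:

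1. Restate the RMQ power as about 85% with 18 practices and about 89% if all 20 are retained. Say that both are t-based (16 and 18 degrees of freedom), at an ICC of 0.1 and with equal practice sizes.
2. For the EQ-5D-5L, state the ICC and the two autocorrelations used and whether 18 or 20 practices are assumed, then recompute on the same t basis. If the RMQ values were used, the figures are about 81% with 18 practices and 86% with 20.
3. Optionally, print the RMQ effect size as 0.44, to the same precision as the 0.42 given for the EQ-5D-5L.

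The cost is a change of text. No patients or practices are added, and the design and analysis stay as they are. The stated power becomes somewhat less favourable.

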4.8.2. Health outcome data analysis

All analyses will be by intention-to-treat. Our primary outcome (RMQ) with repeated measures at 0, 2-week, 6-weeks, 3-, 6-, 9-, and 12-months will be analysed using linear mixed-effects regression, estimated using restricted maximum likelihood (REML). The model will include fixed effects for time, group by time interaction (omitting the group main effect to ensure baseline differences are constrained to 0), factors used in the covariate constrained allocation procedure, and other prespecified covariates associated with LBP-related disability. The correlation in repeated measures on the same participant will be modelled using a suitable covariance structure, identified using information criteria (AIC/BIC) and likelihood ratio tests. To account for clustering within practices, site will be modelled as a random effect. The intervention effect will be obtained as the adjusted least square mean difference between arms at 12-months together with 95% confidence intervals. Secondary comparisons will be obtained using least square mean differences at intermediate time points. The use of REML estimation under an assumption of missing at random allows the use of all available data without the need for multiple imputation. To examine the risk of bias due to missing data, we will compare characteristics of those remaining and those lost to follow-up to identify factors associated with attrition and adjust for any such factors as covariates. Secondary outcomes (remaining individual health outcomes, healthcare access, GP workload, healthcare utilisation, and lost work) that are continuous will be analysed as described for the primary outcome, while secondary outcomes that are categorical will be analysed using generalised linear mixed effects modelling with binomial, Poisson, or negative binomial distribution. We will analyse results after completion of 12-month follow-up with no planned interim analyses.

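### The primary model's single site random effect holds site effects constant over visits, against the planned autocorrelation of 0.5; reported standard errors would be about one third of their true size

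*Protocol*

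**What the plan says.** Protocol section 4.8.2 fits RMQ at all seven times, baseline included, in one linear mixed model by REML. The fixed effects are time and group-by-time without a group main effect, so the arms are constrained to be equal at baseline. The covariance is described in two sentences, one for each level:

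- Patient level: "The correlation in repeated measures on the same participant will be modelled using a suitable covariance structure", chosen by information criteria and likelihood ratio tests.
- Site level: "To account for clustering within practices, site will be modelled as a random effect".

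No site-by-time term or site-level correlation over visits is stated. The same approach is carried over to the continuous secondary outcomes.

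Section 4.8.1 sizes the trial "based on an ANCOVA analysis for the primary outcome (RMQ) at 3 months with the baseline measurement of RMQ as a covariate". Among its inputs is a cluster "autocorrelation coefficient (correlation between cluster means at baseline and follow-up) of 0.5".

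**The concern.** A single site random effect in a repeated-measures model adds the same amount to every visit at that site, which is a site-level autocorrelation of 1. The planning value of 0.5 says that half of the site variance changes between baseline and follow-up. The model has no term for that half. The patient-level covariance cannot supply one, however flexible it is, because it is independent between patients of the same site.

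The constrained baseline makes this serious. Baseline is part of the outcome vector and carries no group effect, so the model learns each site's effect from baseline and subtracts nearly all of it from follow-up. What remains is treated as patient-level noise averaged over many patients, and the standard error comes out close to that of an individually randomised trial. At stake is the validity of the primary p-value and confidence interval: ignoring variation at the level of the randomised unit is the error a cluster trial must avoid. An ANCOVA at one follow-up, as used for the sample size, would not have this fault, because one site intercept is enough there.

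**Working it through.** **Inputs (section 4.8.1).** SD 5.7, so total variance 32.49; difference 2.5; two-sided alpha 0.05; ICC 0.1; site autocorrelation (CAC) 0.5; individual autocorrelation (IAC) 0.6; m = 62 patients per site; 9 sites per arm. Assumptions added here: equal site sizes, no missing data, and 0.6 read as the within-site correlation.

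**1. The plan's own figure.** The plan states that "A total of 18 clusters (9 per arm) with an average of 62 participants per practice (i.e. total 1,116 participants) achieves 90% power".

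- r = [m·ICC·CAC + (1−ICC)·IAC] / [1+(m−1)·ICC] = (3.1 + 0.54)/7.1 = 0.513
- Sites per arm = 2(1.960+1.282)²(5.7/2.5)² × 7.1 × (1−0.263)/62 = 9.22
- SE at 9 per arm = √[2 × 32.49 × 7.1 × 0.737/(62 × 9)] = 0.781
- Power = Φ(2.5/0.781 − 1.96) = 89.3%

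The stated 90% is reproduced, and it depends on the CAC of 0.5.

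**2. Why the analysis model reports less, by hand.** Work with site means at baseline and follow-up.

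- Patient part: variance 0.9 × 32.49/62 = 0.472; covariance 0.6 × 0.472 = 0.283.
- True site part: variance 3.249 at each time; covariance 0.5 × 3.249 = 1.624.
- True site means: variance 3.721, covariance 1.907.

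With one site intercept, the fitted site variance in the simulations below averages about 2.44, and it serves as both variance and covariance.

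- The model therefore believes: variance 2.44 + 0.472 = 2.912; covariance 2.44 + 0.283 = 2.723.
- Weight on baseline: 2.723/2.912 = 0.935. The true structure would give 1.907/3.721 = 0.513.
- Residual variance the model believes: 2.912 − 2.723²/2.912 = 0.365, so SE = √(2 × 0.365/9) = 0.285.
- Actual variance of that contrast: 3.721 × (1 + 0.935²) − 2 × 0.935 × 1.907 = 3.41, so SE = √(2 × 3.41/9) = 0.87.
- Ratio 0.285/0.87 = 0.33.

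**3. Simulation with the variances estimated.** REML, constrained baseline, unstructured patient covariance, site intercept only, no treatment effect:

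| Design | Mean reported SE | True SE | Ratio | Type I error (z) |
|---|---|---|---|---|
| 9 × 62 per arm, 2 times | 0.300 | 0.860 | 0.35 | 50% |
| 10 × 78 per arm, 2 times | 0.255 | 0.807 | 0.32 | 51% |
| 9 × 62, 7 times, constant correlations | 0.299 | 0.857 | 0.35 | 45% |
| 9 × 62, 7 times, decaying correlations | 0.297 | 0.854 | 0.35 | 46% |

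The seven-visit rows rest on 100 simulated trials each. With 20 sites of 62, two simulations gave 0.29 against 0.83 and 0.29 against 0.79, and a type I error of 50% to 52% (z) or 47% (t, 18 df). As a check, a ratio of 0.35 implies a type I error of 2 × [1 − Φ(1.96 × 0.35)] = 49%.

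**4. Sensitivity (9 × 62 per arm, one input changed at a time).**

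| ICC | CAC | Ratio | Type I error (z) |
|---|---|---|---|
| 0.1 | 0.7 | 0.43 | 40% |
| 0.1 | 0.8 | 0.50 | 32% |
| 0.1 | 0.9 | 0.63 | 21% |
| 0.1 | 0.95 | 0.76 | 13% |
| 0.1 | 1.0 | 1.02 | 6% |
| 0.05 | 0.5 | 0.47 | 37% |
| 0.01 | 0.5 | 0.78 | 12% |

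The fault disappears at a CAC of 1, which identifies the missing site-by-time variance as its cause.

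**5. With a site-by-time random effect added (9 × 62 per arm, 1,000 trials).** Mean reported SE 0.76 against a true 0.81, ratio 0.93; type I error 7.5% with z and 6.0% with t on 16 df. The reported SE is close to the planning value of 0.78.

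**The case against.** The protocol does not say that the site effect is the only one or that it is constant, and site-level covariance and degrees of freedom are often settled in an SAP, which is not at hand. That is right for the degrees of freedom: their absence is not an error, and they appear below as a recommendation. It does not dispose of the site term. The protocol states that term, reserves the flexible covariance for repeated measures on the same participant, and so describes a model at odds with its own sample size. A statistician following the text would fit one intercept.

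The stronger point concerns size. The ICC of 0.1 is called conservative, and one third is the figure at the planning values. If a lower ICC and a higher CAC hold together, the damage is much smaller. With 20 sites and t on 18 df, assumed values of ICC 0.05 and CAC 0.8 give a ratio of 0.63 and 18% type I error; ICC 0.02 and CAC 0.9 give 0.92 and 5%. This stands as a limit on the magnitude. It does not rescue the model, whose validity would then depend on the planning assumptions being wrong in a favourable direction. Covariates could also reduce the between-site variance, by an amount the document does not let one estimate.

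**Conclusion.** The concern holds. As written, the primary model contradicts the site autocorrelation that sized the trial. At the planning values its standard error is 0.32 to 0.36 of the true one, and a nominal 5% test rejects a true null hypothesis in roughly half of trials. The figure rests on ICC 0.1 and CAC 0.5, equal site sizes and complete data; with lower ICC and higher CAC the effect runs from severe to negligible. It applies at every follow-up visit, so it does not depend on whether 3 or 12 months is the primary time point, and it extends to the continuous secondary outcomes. It should be corrected before any analysis.

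**What to change.** Replace the site sentence in section 4.8.2 with wording such as: *Clustering will be modelled with random effects for site and for site-by-time, with Kenward-Roger or Satterthwaite degrees of freedom reflecting the 20 sites.* Apply the same to the secondary outcomes. Another site-level covariance over visits would also serve, but a fully unstructured one has 7 × 8/2 = 28 parameters for 20 sites, so the two-component form is more practical. The SAP should carry the same text.

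No patients, sites or visits are added. Confidence intervals widen to about the standard error already assumed: 0.78 with 18 sites of 62, or 0.74 with 20. The t reference has a modest cost that the normal-based calculation does not show: power is 85.2% with 18 sites (16 df) and 89.1% if all 20 are retained (18 df).

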1. SUMMARY

Study title: ConnectBack Trial – Creating Team-Based care for a new primary care model for low back pain: A cluster randomised trial

Protocol version: 2024/1.8

Objectives:

Overarching objective

To evaluate whether integrating a musculoskeletal (MSK) clinician (physiotherapist/chiropractor) within primary care teams for people with low back pain (LBP) and making this clinician available to LBP patients as an early point of contact, will improve outcomes.

Specific objectives

The specific aims are to determine whether a new model of care for people presenting to primary care with LBP, incorporating a team-based approach, is more effective than usual general practitioner (GP)-led care, evaluated over a one-year period, for:

- 1) disability (primary outcome at 3 months), pain intensity, quality of life, global rating of change, patient satisfaction, and adverse events.
- 2) health system and societal outcomes, including healthcare access, GP workload, emergency department visits, diagnostic imaging, opioid medications used, and missed work.
- 3) cost-effectiveness.

Further, a process evaluation will assess the implementation of the model of care and the perspectives of patients and primary care providers towards the model.

Study design:

The trial is a parallel arm cluster randomised trial (CRT) with 20 primary care practices randomised 1:1 to either an innovative primary care model of care incorporating a team-based approach, or to usual GP-led care for low back pain (LBP).

Planned sample size:

Twenty GP practice sites will recruit a total of 1,560 participants.

Selection criteria:

Practice inclusion criteria: At least 2 GPs from the practice are willing to participate; and the practice can accommodate a trial MSK clinician to coordinate patient treatment.

Practice exclusion criteria: The practice already has an integrated MSK clinician (physiotherapist or chiropractor) onsite.

GP inclusion criteria: GP works in an eligible practice, and the GP is willing for their practice to be randomised to the intervention or usual care arm.

GP exclusion criteria: working in a practice that already has a physiotherapist/chiropractor integrated into the team.

Patient inclusion criteria: adults (≥ 18 years) with LBP of any duration (with or without associated leg pain), who can read, write, and speak in English.

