3. PROJECT AIMS

The overarching goal of this CRT is to evaluate whether integrating a MSK clinician (physiotherapist/chiropractor) within primary care teams for people with LBP and making this clinician available to LBP patients as an early point of contact, will improve outcomes. The specific aims are to determine whether a new model of care for people presenting to primary care with LBP, incorporating a team-based approach, is more effective than usual GP-led care, evaluated over a one-year period, for:

- 1) disability (primary outcome at 3 months), pain intensity, quality of life, global rating of change, patient satisfaction, and adverse events.
- 2) health system and societal outcomes, including healthcare access, GP workload, emergency department visits, diagnostic imaging, opioid medications used, and missed work.
- 3) cost-effectiveness.

Further, a process evaluation will assess the implementation of the model of care and the perspectives of patients and primary care providers towards the model. This current ethics application does not include the process evaluation; we will submit the ethics application for the process evaluation at a later date.

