4.5. Outcome Measures

Self-reported patient outcome measures will be collected at baseline, 2-weeks, 6 weeks, 3-, 6-, 9-, and 12-months from the initial visit with a primary comparison at 3-months. See the Table for the timing of each of the outcomes. All these outcomes will be collected using REDCap and will be completed by participating patients. If they are unable to enter their information directly, a study RA will assist them to do this over the telephone/Zoom.

See Appendix – Data collection forms for all outcomes that will be used for this study and the data collection time points.

Table: Patient participant outcome measures and timing

Outcome measure	Baseline	2 weeks	6 weeks	3 months (primary comparison)	6 months	9 months	12 months
Individual health outcomes							
Pain intensity questions based on Brief Pain Inventory	X	X	X	X	X	X	X
Roland Morris Questionnaire (RMQ)	X	X	X	X	X	X	X
EQ-5D-5L	X	X	X	X	X	X	X
PSEQ	X	X	X	X	X	X	X
TSK	X	X	X	X	X	X	X
GROC		X	X	X	X	X	X
Patient satisfaction		X	X	X	X	X	X
Adverse events		X	X	X	X	X	X
Health system, societal and cost outcomes							
Healthcare utilisation	X			X	X	X	X
Absenteeism/Presenteeism (iPCQ)	X			X	X	X	X

NB: EQ-5D-5L = European Quality of Life five dimensions: mobility, self-care, usual activities, pain/discomfort and anxiety/depression questionnaire. PSEQ = Patient Self-Efficacy Questionnaire; TSK = Tampa Scale for Kinesiophobia; GROC = global rating of change. iPCQ = Productivity Cost Questionnaire

4.5.1. Primary Outcome Measure:

Self-reported LBP disability using the Roland Morris Questionnaire (RMQ) ¹⁴ measured at 3 months. Disability and function are considered the most important outcomes for people with LBP ¹⁵.

4.5.2. Secondary Outcome Measures:

4.5.2.1. Individual health outcomes:

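### Section 4.8.2 takes the intervention effect on RMQ at 12 months, while every other section that names a primary time point, including the sample size, says 3 months

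*Protocol*

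**What the plan says.** Five places in the protocol put the primary comparison at 3 months:

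- Section 1 (Summary), specific objectives: "disability (primary outcome at 3 months), pain intensity, quality of life".
- Section 3 (Project aims) repeats this objective.
- Section 4.5 (Outcome Measures), on the schedule of questionnaires: "from the initial visit with a primary comparison at 3-months". The 3-month column of the outcome table carries the same label.
- Section 4.5.1 defines the primary outcome as RMQ disability "measured at 3 months. Disability and function are considered the most important outcomes".
- Section 4.8.1 (Sample size calculation) bases the number of clusters on an "ANCOVA analysis for the primary outcome (RMQ) at 3 months with the baseline measurement of RMQ as a covariate".

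Section 4.8.2 (Health outcome data analysis) describes a linear mixed model for RMQ, named there as the primary outcome, with measurements from baseline to 12 months. It then says: "The intervention effect will be obtained as the adjusted least square mean difference between arms at 12-months together with 95% confidence intervals". The next sentence is: "Secondary comparisons will be obtained using least square mean differences at intermediate time points". The section ends by placing the analysis after 12-month follow-up, with no interim analysis.

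**The concern.** Three months lies between baseline and 12 months, so under 4.8.2 it is one of the intermediate time points and its contrast is secondary. The section that an analyst would implement therefore contradicts the section that defines the primary outcome and the section that sizes the trial. Nothing in the protocol reconciles them.

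The model gives a group difference at every follow-up time, and all of them become available at once, after 12 months. If the 3-month and 12-month results disagree, the trial could be called positive or negative according to which section is cited. The outcome is self-reported, and section 4.3 states that patients, GPs and MSK clinicians are not blinded, so a clear prior commitment to one contrast matters all the more.

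**Working it through.** **1. The sections side by side**

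| Section | Time point given the main role |
|---|---|
| 1 Summary | 3 months |
| 3 Project aims | 3 months |
| 4.5 text and table heading | 3 months |
| 4.5.1 Primary outcome | 3 months |
| 4.8.1 Sample size | 3 months |
| 4.8.2 Analysis | 12 months, with intermediate times secondary |

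Section 4.8.1 also mentions 12 months for attrition, and 4.8.2 mentions it for the timing of the analysis. Neither reference defines a primary time point. The conflict is in the current text, not in the amendment list.

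**2. Reproducing the stated power at 3 months**

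Inputs from 4.8.1: 9 clusters per arm, m = 62 per cluster, difference 2.5, SD 5.7, ICC 0.1, cluster autocorrelation (CAC) 0.5, individual autocorrelation (IAC) 0.6, two-sided alpha 0.05. The formulas are those of the ANCOVA method for cluster trials that 4.8.1 names.

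- Design effect before covariate adjustment: 1 + 61 × 0.1 = 7.1.
- Correlation of cluster means between baseline and follow-up: r = (62 × 0.1 / 7.1) × 0.5 + (0.9 / 7.1) × 0.6 = 0.513.
- Design effect after adjustment: 7.1 × (1 − 0.513²) = 5.234.
- Standard error: 5.7 × √(2 × 5.234 / 558) = 0.781, where 558 = 9 × 62.
- Power, normal approximation: Φ(2.5 / 0.781 − 1.96) = 89.3%, against the stated 90%.
- Recruitment: 62 / 0.8 = 77.5, rounded up to 78; 20 × 78 = 1,560, as stated.

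The sample size therefore belongs to the 3-month comparison and agrees with its own inputs.

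**3. What is known about power at 12 months**

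The protocol gives no correlations specific to 12 months. Keeping the difference, SD, ICC and cluster numbers, and assuming lower correlations over the longer interval, power by the same normal approximation is:

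| CAC (assumed) | IAC (assumed) | Power |
|---|---|---|
| 0.5 | 0.6 | 89.3% |
| 0.4 | 0.5 | 85.5% |
| 0.3 | 0.4 | 82.5% |
| 0.2 | 0.3 | 80.3% |

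**4. False-positive risk if either contrast could be claimed**

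Let Z₁ and Z₂ be the test statistics at 3 and 12 months, with no true effect at either time. The risk is P(|Z₁| > 1.96 or |Z₂| > 1.96) under a bivariate normal distribution. Independent tests would give 1 − 0.95² = 9.75%. The correlation between the two estimates is not in the protocol and is assumed:

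| Correlation (assumed) | Risk of at least one false positive |
|---|---|
| 0.3 | 9.5% |
| 0.5 | 9.1% |
| 0.7 | 8.3% |
| 0.8 | 7.8% |

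**The case against.** The strongest reply is that the protocol does define its primary endpoint. Section 4.5.1 is explicit and the sample size agrees with it, whereas the 12-month sentence never uses the word primary. It may be a drafting remnant. The same paragraph of 4.8.2 refers to covariate-constrained allocation, while section 4.2 describes stratified permuted blocks, so 4.8.2 does not seem to have been brought fully up to date. Read this way, no one is free to choose a primary test, and the figure of about 9% describes a selection rule that the protocol does not plan. Nor would a 12-month test be badly underpowered, because recruitment already allows for 20% attrition at 12 months.

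Much of this stands. A remnant is plausible, 3 months is the best-supported intention, the 9% is a worst case, and what 12 months lacks is a stated justification rather than adequate numbers. But the contradiction remains. Section 4.8.2 names a single intervention effect for the primary outcome and labels the intermediate contrasts secondary, so it cannot be read as giving 3 months primary status. A statistical analysis plan does not settle the matter by itself. One written from 4.8.2 would inherit the 12-month effect, and one written from 4.5.1 would depart from the protocol's analysis section.

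**Conclusion.** The concern holds and must be corrected before outcome data are analysed. The protocol's analysis section contradicts its own primary outcome definition and sample size on the time of the primary comparison.

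The contradiction itself rests on no assumption. Its size does. The rise from 5% to about 9% applies only if whichever of the two contrasts is significant may be presented as primary and there is no effect at either time. For 12 months the protocol states no power. The 80.3% to 89.3% obtained here depends on assumed 12-month correlations, with the difference, SD and ICC unchanged. The 3-month sample size is sound as a match to its stated inputs and is not in question.

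**What to change.** Replace the two sentences on time points in 4.8.2 with: *The primary intervention effect is the adjusted mean difference in RMQ between arms at 3 months, with its 95% confidence interval. Differences at 2 weeks, 6 weeks, 6, 9 and 12 months are secondary.* Use the same definition in the statistical analysis plan.

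The cost is a short protocol amendment. The model, the data collection and the sample size stay as they are.

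The sponsor should confirm that 3 months is intended. If it is 12 months, sections 1, 3, 4.5 (text and table heading), 4.5.1 and 4.8.1 all have to change, and the power has to be justified again with correlations between baseline and 12 months. In either case the choice should be dated and recorded before any comparison of the arms is seen.
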